- a. Does your YNHH privilege delineation currently include the **specific procedure** that you will perform? Yes No
- b. Will you be using any new equipment or equipment that you have not used in the past for this procedure? Yes No
- c. Will a novel approach using existing equipment be applied? Yes No

If you answered "no" to question 4a, or "yes" to question 4b or c, please contact the YNHH Department of Physician Services ([name]) for prior approval before commencing with your research protocol.

IMPORTANT REMINDER ABOUT RESEARCH AT YNHH

Please note that if this protocol includes Yale-New Haven Hospital patients, including patients at the HRU, the Principal Investigator and any co-investigators who are physicians or mid-level practitioners (includes PAs, APRNs, psychologists and speech pathologists) who may have direct patient contact with patients on YNHH premises must have medical staff appointment and appropriate clinical privileges at YNHH. If you are uncertain whether the study personnel meet the criteria, please telephone the Physician Services Department at [contact]. **By submitting this protocol as a PI, you attest that you and any co-investigator who may have patient contact has a medical staff appointment and appropriate clinical privileges at YNHH.**

SECTION I: RESEARCH PLAN

1. **Statement of Purpose:** State the scientific aim(s) of the study, or the hypotheses to be tested.

We propose to examine, in 172 women newly diagnosed with Stage I-III breast cancer who are not practicing the dietary and lifestyle guidelines, and who will receive neoadjuvant or adjuvant chemotherapy as part of their treatment, the effect of a 1-year dietary and physical activity guidelines intervention vs. usual care on the breast cancer outcomes described below. Women will be enrolled either before beginning chemotherapy or following the first chemotherapy infusion but prior to the second chemotherapy infusion (Time 0). Follow up visits will occur post chemotherapy (Time 1), at one-year post-diagnosis (Time 2), at two years post-diagnosis (Time 3) and at five years post-diagnosis.

Primary Endpoints: Adherence to Breast Cancer Treatments

Aim 1a: Chemotherapy completion rates (dose amount, number of dose reductions and dose delays)

Aim 1b: Adherence to endocrine therapy in women taking tamoxifen or Aromatase Inhibitors (AIs) at 12- and 24-months after enrollment

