a) **Experimental Design:** The proposed study is a randomized trial evaluating the impact of a dietary and physical activity guidelines intervention vs. usual care on adherence to breast cancer treatments, body composition, and changes in biomarkers in 172 women newly diagnosed with breast cancer who will receive neoadjuvant or adjuvant chemotherapy as part of their treatment. The intervention will be conducted in person in the breast clinic at Smilow Cancer Hospital/Smilow Care Center and/or via telephone/video over one-year. When possible, assessments (4 in total) will be completed at a study baseline clinic visit (after diagnosis for women receiving neoadjuvant chemotherapy and after breast surgery for women receiving adjuvant chemotherapy, but prior to the second chemotherapy infusion) and post chemotherapy, at 1- and 2-yrs post-diagnosis. If not possible for a patient to travel to New Haven for the in-person study assessments, the patient will complete online or/and hard copy study questionnaires. These may be administered by phone. The assessments conducted at the in-person visit are optional at all timepoints. The assessments include: physical exam (height, weight, waist and hip circumference), DXA scan, blood and urine collection, grip strength and carotenoid assessment. Following publication of the initial primary results the manuscript will be mailed to all study participants. Participants who consented to be recontacted will be asked if they are willing to participate in a 5-year follow. Five-year follow up will include assessment of dietary intake, physical activity, and quality of life, similar to these 1- and 2-year assessments. Data regarding breast cancer recurrence, mortality and medical usage will be abstracted from the EMR.

Study Population: We will enroll 172 women over 2.5 years (~ 8-9 women/month). Women will be enrolled prior to their the second neoadjuvant or adjuvant chemotherapy session. Given treatments are often of a longer duration for stage IV (which includes recurrent breast cancer) breast cancer, women with stage IV will not be eligible. Patients with recurrent cancer, independent of whether they have received chemotherapy at the time of initial diagnosis, or the time that has elapsed since the initial diagnosis, are eligible. The treatment of the recurrent cancer must be intended to be curative.

Table 1. Eligibility Criteria

Inclusion Criteria:

- Diagnosed with Stage I-III breast cancer

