In July 2020, all women who are or who have been (if they agreed to future contact as indicated on the study consent form) participants in LEANer will be invited via email to complete an online or hard copy survey regarding the effect of the coronavirus epidemic on their cancer care, and their mental health, diet and physical activity. A link to the survey, which will be hosted on the Qualtrics platform, will be included in the email invitation with instructions on how to get the hard copy questionnaire if desired. The survey will take approximately 10-15 minutes to complete. A study staff member will follow up by email, text message or phone to confirm receipt of the invitation to complete the survey and answer any questions.

Newsletter: A newsletter will be mailed to all participants at 6-monthly intervals while enrolled in the study informing them of the progress of the study and providing relevant information with regard to breast cancer survivorship issues.

All assessments denoted * above are conducted at the in-person visits and are optional.

d) Randomization: Participants will be randomized into one of 2 study arms using a random permuted block design of varying block size in a 1:1 ratio (N=125 to intervention, 125 to usual care). To ensure participants with similar characteristics are equivalently assigned to the 2 groups, we will stratify on the following factors that may be associated with some of the study endpoints:

- i) chemotherapy regimen (≤ 4 cycles vs. >4 cycles)
- ii) hormone receptor status (ER/PR+ or not)
- iii) HER2 status (HER2+ve or not)

Resulting in six strata.:

- a) HR/PR+ve, HER2-ve, ≤ 4 cycles
- b) HR/PR+ve, HER2-ve, >4 cycles
- c) HR/PR-ve, HER2-ve, ≤ 4 cycles
- d) HR/PR-ve, HER2-ve, >4 cycles
- e) HR/PR+ve, HER2+ve, >4 cycles
- f) HR/PR-ve, HER2+ve, >4 cycles

The following study personnel will be masked to participant study arm: clinic medical staff performing the DXA scan and laboratory analysis.

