Participants who report that they have discontinued taking tamoxifen or AI will also be classified as nonadherent to endocrine therapy. For patients who may be lost to follow-up, we will obtain prescription refill data as an endpoint of adherence to endocrine therapy. For the endocrine

therapy aim, we will compare the crude adherence rates using simple logistic regression. Multivariate logistic regression will serve as supportive analyses including covariate adjustments – which are similar to the primary analysis above.

The secondary aims will be performed using Mixed Model Repeated Measures analysis incorporating Analysis of Covariance, where each woman's changes in outcome (follow-up measure – baseline) will be modeled as a function of treatment and time with a covariate included for the baseline value. Prior to fitting models, we will perform exploratory data analyses focusing on the distributions of biological markers by time and intervention group, assessing the appropriateness of log-transformation.

All hypotheses will be tested according to the intention-to-treat philosophy in which all randomized participants will be grouped according to their intervention assignment at randomization, regardless of compliance or adherence to the study. Statistical significance will be defined as $p < 0.05$, 2-sided. Since we have multiple outcomes, we will consider using a Bonferroni correction.

Age, menopausal status, race/ethnicity, BMI at diagnosis, disease stage, type of surgery, type of chemotherapy, radiation therapy, hormone receptor status, endocrine therapy, reconstructive surgery, type 2 diabetes, and smoking status will be examined as covariates. We will explore effect modification by menopausal status at diagnosis, hormone receptor status, and endocrine therapy.

We will further explore intervention effects on study endpoints by stratifying by adherence to diet and physical activity guidelines with a four-level category (e.g., met diet recommendations, met physical activity, met both diet and physical activity recommendations, or met neither recommendation). This analysis will allow us to better understand the role of diet vs. exercise on study endpoints.

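### Baseline precedes surgery in neoadjuvant women and follows it in adjuvant women, yet treatment setting is not in the secondary-outcome model: a modest, cheaply recovered loss of precision

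*Combined protocol and SAP*

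**What the plan says.** Section I, item 3(a) (Experimental Design) times the baseline clinic visit "after diagnosis for women receiving neoadjuvant chemotherapy and after breast surgery for women receiving adjuvant chemotherapy", in both cases before the second infusion. Later assessments follow chemotherapy and fall at 1 and 2 years after diagnosis.

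Item 3(d) (Randomization) states that "we will stratify on the following factors that may be associated with some of the study endpoints". It names three: planned number of cycles (four or fewer against more), hormone receptor status and HER2 status. Setting is not among them.

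Item 12 (Statistical Considerations) analyses the secondary aims by a repeated-measures mixed model in which each woman's change "will be modeled as a function of treatment and time with a covariate included for the baseline value". A separate list of variables is to be examined as covariates. It includes "disease stage, type of surgery, type of chemotherapy, radiation therapy, hormone receptor status, endocrine therapy, reconstructive surgery", but neither treatment setting nor the timing of surgery relative to baseline. Setting is also not among the effect modifiers to be explored (menopausal status, hormone receptor status, endocrine therapy).

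**The concern.** In an adjuvant woman the baseline value already carries the effect of recent surgery, and later visits show recovery. In a neoadjuvant woman the baseline is free of surgery, and the operation falls before the 1- and 2-year visits. One time course and one baseline slope are then fitted to two groups whose change scores mean different things.

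The baseline covariate cannot repair this. Two women with the same baseline value but different settings have different expected follow-up values, because only one of them has surgery still to come. Without a setting term, that difference stays in the residual variance.

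What is at stake is the width of the confidence intervals for secondary outcomes analysed as change and sensitive to surgery. Quality of life and CRP are the plausible cases among the listed secondary endpoints.

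**Working it through.** **The plan's own secondary figure.** Item 12 gives a sample size for insulin: difference 3.0, SD 8.0, 112 per group. With two-sided alpha 0.05 and 80% power (the power is not stated, but 80% reproduces the figure):

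n per group = 2 × (1.960 + 0.842)² × 8.0² / 3.0² = 111.6, so 112.

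At the trial's actual 86 per arm the same inputs give 69.1% power. This is used below only as a scale for what a given variance inflation does to power. Nothing in the documents shows that surgery shifts insulin.

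**Inputs for the setting effect.** None is in the documents; all are assumptions.
- p, neoadjuvant share: 0.3 to 0.5, with q = p(1 − p) = 0.21 to 0.25
- r, within-setting correlation of baseline and follow-up: 0.5 to 0.6
- d, shift of the baseline value in adjuvant women: 0.3 to 0.5 SD
- g, shift of the 1-year value in neoadjuvant women relative to adjuvant women: 0 to 0.1 SD, because by then both groups have had surgery and g reflects only the difference in time since the operation

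**Formula.** The within-setting variance is set to 1. With baseline as a covariate, modelling change or the follow-up value gives the same residual variance.
- Baseline only: V0 = (1 + q g²) − (r − q d g)² / (1 + q d²)
- With setting added: V1 = 1 − r²
- Inflation = V0 / V1; information lost from N women = N × (1 − V1/V0)

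**Lowest case** (p = 0.3, r = 0.5, d = 0.3, g = 0): V0 = 1 − 0.25/1.0189 = 0.7546; V1 = 0.75; ratio 1.006.

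**Highest case in the central range** (p = 0.5, r = 0.6, d = 0.5, g = 0.1): V0 = 1.0025 − 0.5875²/1.0625 = 0.6776; V1 = 0.64; ratio 1.059.

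| d | g | Variance inflation | Women out of 133 |
|---|---|---|---|
| 0.3 | 0 | 0.6-1.2% | 1-2 |
| 0.5 | 0 | 1.7-3.3% | 2-4 |
| 0.3 | 0.1 | 1.7-3.0% | 2-4 |
| 0.5 | 0.1 | 3.3-5.9% | 4-7 |
| 0.3 | 0.3 | 5.6-8.8% | 7-11 |
| 0.5 | 0.5 | 15.0-23.5% | 17-25 |

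The 133 is the Yale enrolment target and fits CRP, since blood is drawn only at Yale. Quality of life is collected by questionnaire from all 172 women. There the first four rows span 172 × (1 − 1/1.006) ≈ 1 to 172 × (1 − 1/1.059) ≈ 10 women.

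**Cross-check.** Given baseline, the settings differ by (g + r d)/√(1 − r²) residual SDs. That is 0.15/0.866 = 0.17 in the lowest case and 0.40/0.80 = 0.50 in the highest central case. The simpler formula 1 + q × (difference)² gives 1.006 and 1.063, close to the exact 1.006 and 1.059.

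**On the power scale.** An outcome with 69.1% power at 86 per arm would fall to about 66.6% at an inflation of 1.059, and to about 60% at 1.235.

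**Where it does not matter.** With the weight figures in item 12 (5.6 against 1.7 kg, SDs 4.2 and 3.7), power at 86 per arm stays above 99.9% even if the settings differ by 4 kg.

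**The case against.** The strongest reply is that the plan already lists type of surgery, reconstructive surgery and type of chemotherapy as candidate covariates, so part of the variation may be absorbed. This stands only in part. The list is to be examined, with no commitment to include anything; type of chemotherapy is undefined; and no item records whether surgery preceded baseline. Type of surgery is also settled after randomization in neoadjuvant women. The protocol's background section says that neoadjuvant treatment raises breast-conserving rates through tumor shrinkage, and Aim 5 studies tumor response by arm. Adjusting for it could remove part of an intervention effect. Planned setting has no such problem.

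A second reply is that the post-chemotherapy visit may precede surgery in neoadjuvant women, in which case their change at that visit contains no surgical effect. No text places that visit relative to surgery, so the reply cannot be dismissed. It argues for letting the setting effect differ by visit.

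Stronger readings are tempting, but the documents do not support them:
- **That the arm comparison is biased.** Setting is balanced between arms in expectation. Chance imbalance (an SD of about 7 to 8 percentage points in neoadjuvant share at 86 per arm) is already reflected in the standard error and is not a separate harm.
- **That the loss is 6-24%.** This needs the surgical shift at 1 year to be as large as the shift at a baseline taken soon after surgery. That sits poorly with recovery: chemotherapy lasts about 3 to 5 months, so the 1-year visit probably comes months after the operation (an assumption, since no interval is given).
- **That every secondary aim suffers.** No effect is shown for weight, bone density, insulin, NCS1 or carotenoids.

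**Conclusion.** The concern holds as a minor point about precision. Baseline falls on opposite sides of surgery in the two settings, and neither the strata, the stated model nor the covariate list captures this. Under the assumed shares, correlations and shifts, the cost is roughly 0.6-6% of residual variance for outcomes that surgery plausibly affects. The upper band of 6-24% applies only if the 1-year shift equals the baseline shift. Every input to these ranges is assumed. Relative dose intensity, endocrine adherence and pathologic complete response are not changes from baseline and are untouched.

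**What to change.** In item 12, add planned treatment setting at randomization (neoadjuvant or adjuvant) and setting-by-visit as fixed terms in the repeated-measures model for secondary outcomes analysed as change, in preference to type of surgery. State when the post-chemotherapy visit falls relative to surgery in neoadjuvant women.

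A baseline-by-setting term is optional: the calculation uses one common correlation and gives no support for it.

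The cost is one sentence and a few model degrees of freedom. The trial needs setting anyway, to time the baseline visit and to identify the women assessed for pathologic complete response. One detail to settle is that the randomization data listed for Columbia women (planned sessions, hormone receptor and HER2 status) do not include setting, so planned setting should be recorded at entry or taken from the released records. If the secondary outcomes have already been analysed, label the added model a sensitivity analysis.

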A recruitment flyer will be posted and made available to patients at the Breast Cancer Program of the Herbert Irving Comprehensive Cancer Center at Columbia University; the leader of the Breast Cancer Program, [name], is a consultant on the LEANer study. Interested patients will be asked to contact Yale study personnel, who will describe the study in detail and screen for eligibility. Screening will include collection of data on cancer stage (Stage IV patients are ineligible) and treatment (patients are ineligible if they are not prescribed chemotherapy) in addition to the standard screening data (e.g. minutes per week of exercise). Patients who consent to the study will be asked to sign a medical record release form to allow collection of data on breast cancer diagnosis and treatment, including prescribed chemotherapy regimen and completion of chemotherapy (e.g. dose reductions, delays, and reasons for dose reductions and delays). Patients relevant medical records will be requested at the end of chemotherapy. Women who agree to enroll in the study will be required to provide information on number of chemotherapy sessions planned, hormone receptor and HER2 status as this information is required for study randomization.

3. Dana Farber Cancer Institute (DFCI Study Site)

[name] (PI at DFCI) and her staff will identify, screen, recruit, and consent interested and eligible patients. For patients who consent to participate in the study, the patient's name, address and contact information (phone numbers and email address) and disease related information (e.g. stage, hormone receptor and HER2 status, chemotherapy regimen, treatment plan) and screening form will be provided to the Yale study team to enable study randomization. PHI will be transferred by fax or a method of secure file transfer. Women will complete the self-administered questionnaires either online or hard copies will be provided. The Yale team will inform the patient if randomized to usual care or intervention. If the patient is randomized to the intervention arm the Yale dieticians will conduct the intervention as per study protocol, including mailing the intervention material to the patient. Study questionnaires at the post chemotherapy, year-1 and year-2 visits will be completed online or hard copy. No in-person assessments will be conducted. Staff at DFCI will collect chemotherapy completion data following each chemotherapy session.

c) Study Assessments:

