Women will be asked to complete the self-administered study questionnaires prior to the in-person baseline visit. They will be provided a link via email to the online questionnaires or given a hard copy version if preferred.

Assessments	Screening	Baseline	Post-chemo	1-year	2-year	5-year
Screening Questionnaire	X					
Demographic Questionnaire*		X				
Medical History Questionnaire*		X				
Food Frequency Questionnaire		X	X	X	X	X

Phone assessment 24-hour dietary recall – 1-day ^{&1}		X	X	X	X	
Physical Activity Questionnaire		X	X	X	X	X
Patient Global Assessment (SGPGA)	X					
PROMIS quality of life questionnaires(74)		X	X	X	X	X
Prescription Medication		X	X	X	X	X
Adherence to medication questionnaire(75, 76)				X	X	X
Neuropathy – EORTLC QLQ-CIPN20(77)		X	X	X	X	X
Work history			X	X	X	X
Beliefs about Medication Questionnaire(78)				X	X	X
Treatment Satisfaction Questionnaire for Medication(79)				X	X	X
Health Insurance, prescription coverage and prescription refill habits				X	X	X
Medication usage questionnaire				X	X	X
Aromatase Inhibitor/Tamoxifen usage form				X	X	X
Breast Cancer Prevention Trial (BCPT) Symptom Scales (80)		X	X	X	X	X
Brief Pain Index		X	X	X	X	X
Homunculus		X	X	X	X	X
Y5-Lymphedema Questionnaire						X
Supplement intake/over the counter medication *		X	X	X	X	X
Y1 -Lymphedema Questionnaire				X		
Y2- Lymphedema Questionnaire					X	
Satisfaction Questionnaire (Intervention group)				X		
Side-effects and toxicity assessment (PRO-CTCAE™)		X	X			
Chemotherapy delay/dose reduction/reasons (extracted from EPIC EMR)			X			
Grip Strength [%]		X	X	X	X	
EPIC 2YR follow up treatment form					X	

EPIC 5 Year medical usage and breast cancer status abstraction						X
Two Year Follow up Treatment form'					X	
Height and weight measured [%]		X	X	X	X	
Waist and hip circumference measured [%]		X	X	X	X	
Blood collection [%]		X	X	X	X	
DXA scan [%]		X	X	X	X	
Urine collection ^{%@}				X	X	
Urine collection for pregnancy test if applicable prior to DEXA [%]		X	X	X	X	
Stool collection [%]		X	X	X		
Skin carotenoids [%]		X	X	X	X	

*: Part of the Baseline Questionnaire

%: Applicable only to the Yale site when in-person visits are completed. Assessments are optional.

@ Applicable to women who are prescribed an aromatase inhibitor

&: Assessment is optional.

1: Discontinued in August 2020.

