to allow completion. No PHI will be collected by the Fred Hutchinson Cancer Research Center who oversee collection of the FFQ data. No IP addresses are accessed/collected.

Adherence will be assessed via attendance to counseling sessions, as well as by adherence to the diet and physical activity recommendations (assessed via questionnaire at baseline, 1, and 2 years). Women randomized to intervention will also complete a daily log book where they log their daily food, beverages and physical activity (similar to our LEAN and HOPE studies). At each counseling session, the dietitian will review the log book either in person or via phone reporting.

*Weight and Height: Weight and height will be measured by research staff at baseline, post chemotherapy, 1- and 2-years. Participants will be weighed in light clothing, without shoes, rounding up to the nearest 0.1 kg; height will be measured in a standard manner, without shoes, using a stadiometer, rounding up to the nearest 0.1 cm. (Yale in-person visit only)

*Waist and Hip circumference: Waist and hip circumference will be measured at baseline, post-chemotherapy, 1- and 2- years. Each measurement will be taken twice by a research member. (Yale in-person visit only)

*Grip strength will be measured by a simple to administer modified sphygmomanometer (Detecto DHS Series, Northbrook, Illinois). The participant will be asked to squeeze the balloon of the sphygmomanometer three times with maximal force. The average value of three trials for each hand will be recorded. Higher scores (reported in kPa) reflect better grip strength. (Yale in-person visit only)

Pain: Pain will be assessed using the Brief Pain Index (85). Arthralgia will be assessed using a self-assessment tool where patients are asked to mark 'yes' were asked to mark painful joints on a homunculus with circles showing upper and lower extremity joints, and four areas of the back and neck, and additional diagrams of both hands (three joints on each finger and thumb) and both feet (joints at the base of each toe). (76).

Body Image: Body image will be assessed using the PROMIS assessment.

Supplement intake/over the counter medication: These will be assessed using a questionnaire used in prior studies overseen by [name].

Prescription medication: Patients will be asked to self-report current prescription medication usage.

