*Dual Energy X-Ray Absorptiometry (DEXA) scans: DEXA scans will be used to assess body fat percentage, LBM and bone mineral density at baseline, post-chemotherapy, 1- and 2-years. The DEXA measurements will be made with a Hologic scanner (Hologic 4500 with a "Discovery" upgrade, Hologic Inc, Waltham, Mass). All DEXA scans will be evaluated by a radiologist who will be blinded to the intervention group of the participant, and a quality control phantom will be used daily for calibration. Women of childbearing potential will be required to complete a pregnancy test prior to the DEXA scan. Women who are pregnant or intend to get pregnant during the 2-year study time period are excluded from the study. Women who can get pregnant will have a pregnancy test prior to each DEXA scan, if the pregnancy test is positive the woman will not be able to enroll in the study or, if already enrolled, will no

longer be able to participate in the study. However, the data collected prior to pregnancy will be included in the study. (Yale in-person visit only)

Quality of Life (QOL): Women will complete the PROMIS questionnaire to assess physical, emotional, social, and functional well-being as well as fatigue and overall quality of life (74) ,at baseline, post-chemotherapy, 1- 2- and 5-years. (86) They will also complete the EORTLC QLQ- CIPN20 to assess peripheral neuropathy (77), the Breast Cancer Prevention Trial Symptoms Checklist

Work History: Women will complete a questionnaire on work history which can be impacted by chemotherapy (87).

Medical Usage: At the Year 5 timepoint, the following data will be abstracted from the EPIC EMR: breast cancer recurrence, second primary breast cancer, weight, health care utilization.

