For insulin, our previous studies showed a 25-30% effect size (3.0 μ U/mL) and standard deviation of 8.0 μ U/mL, which yields a per group sample size of 112 or total N = 224.24 For weight changes, our LEAN study showed a 7% effect size (5.6 kg) and a SD of 4.2 kg in the intervention group compared to 2% (1.7 kg) and SD of 3.7 kg in usual care (P=0.0004). (24) We will have sufficient statistical power to detect smaller effect size since we will have a larger sample size in the current application.

We will not allow participants who are assigned into usual care cross over to intervention group. However, if 10% of 86 participants who are randomized into intervention arm drop out to usual care, we will have 81% power to detect difference of 18% chemotherapy dose adjustment in intervention vs 34% in controls.

SECTION II: RESEARCH INVOLVING DRUGS, BIOLOGICS, RADIOTRACERS, PLACEBOS AND DEVICES

If this section (or one of its parts, A or B) is not applicable, state N/A and delete the rest of the section.

A. RADIOTRACERS – N/A

B. DRUGS/BIOLOGICS – N/A

B. DEVICES – N/A

SECTION III: RECRUITMENT/CONSENT AND ASSENT PROCEDURES

1. Targeted Enrollment: Give the number of subjects:

- a. Targeted for enrollment at Yale for this protocol: 133
- b. If this is a multi-site study, give the total number of subjects targeted across all sites: 172

2. Indicate recruitment methods below. Attach copies of any recruitment materials that will be used.

- | | | |
|--|--|-------------------------------------|
|  Flyers |  Internet/Web Postings |  Radio |
|  Posters |  Mass E-mail Solicitation |  Telephone |
|  Letter |  Departmental/Center Website |  Television |
|  Medical Record Review* |  Departmental/Center Research Boards |  Newspaper |
|  Departmental/Center Newsletters |  Web-Based Clinical Trial Registries | |
|  YCCI Recruitment database |  Clinicaltrials.gov Registry (do not send materials to HIC) | |

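### Weight and BMI (Aim 2b) are measured up to year 2 only at optional Yale in-person visits, with no medical-record backup, although the plan takes weight from the record at year 5

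*Combined protocol and SAP*

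**What the plan says.** Section I, 1 lists body weight and BMI under Aim 2b as secondary endpoints. Section I, 3(c), Weight and Height, states: "Weight and height will be measured by research staff at baseline, post chemotherapy, 1- and 2-years". The same paragraph limits this to the Yale in-person visit. The height and weight row of the assessment table carries the footnote "Applicable only to the Yale site when in-person visits are completed. Assessments are optional", and Section I, 3(a) adds: "The assessments conducted at the in-person visit are optional at all timepoints".

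Three other provisions narrow the group measured:

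- For DFCI women (Section I, 3(b)): "No in-person assessments will be conducted".
- A note under the assessment table says in-person visits stopped in mid-March 2020, until the institution allowed a restart.
- Section III, 6 lets women who cannot travel, including some from outlying Yale care centers, enrol without in-person visits. They may attend later ones after signing consent.

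The items listed for record abstraction (Section I, 3(c), Medical history) do not include weight or height. For year 5, though, the Medical Usage paragraph says: "the following data will be abstracted from the EPIC EMR: breast cancer recurrence, second primary breast cancer, weight, health care utilization".

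Section I, 12 lists covariates to be examined, beginning "Age, menopausal status, race/ethnicity, BMI at diagnosis, disease stage, type of surgery, type of chemotherapy". Section III, 1 gives "Targeted for enrollment at Yale for this protocol: 133", against 172 across all sites.

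**The concern.** At baseline, post-chemotherapy, year 1 and year 2, the only described source of weight and BMI is a visit that some women cannot attend and the rest may decline. No self-reported or record-based fallback is described. The secondary analysis models change from baseline with the baseline value as covariate, so a woman without a baseline weight contributes no change score, even if she is weighed later.

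Missingness will follow site, calendar time and willingness to travel, so the women analysed for weight are a selected part of those randomized. BMI at diagnosis is also a candidate covariate, and the Background promises adjustment for initial BMI in the pCR analysis. The plan names no BMI source for a woman without a study measurement.

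The gap looks avoidable:

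- Record weight is already accepted at year 5.
- Record routes exist for Yale and DFCI (Section IV) and for Columbia self-referrals through a signed release (Section I, 3(b)).
- Under Usual Care Group, patients see the oncologist at each chemotherapy session, at one and two months afterwards, then every 3 to 6 months up to two years. Clinic contacts therefore fall near all four timepoints.
- The primary endocrine-adherence measure was moved from urine to the medical record because the pandemic limited collection (Section I, 12).

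**Working it through.** **The plan's own sample size.** Section I, 12 gives 86 per arm for a 0.05 difference in RDI, SD 0.10, 90% power, two-sided 0.05. The t-based calculation gives 85.03, rounded up to 86 per arm, or 172. The figure reproduces. No sample size or power figure is given for weight, only a statement that power is sufficient because this trial is larger than LEAN.

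**Share outside Yale.** 172 − 133 = 39; 39/172 = 22.7%. This is a difference of enrolment targets, not a count of missing data.

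**Precision.** With equal SDs, the ratio of confidence-interval widths is √(172/133) = 1.137, about 14% wider if all 133 Yale women are measured. If record weights in the other 39 had an SD 20% larger (an assumption), the average variance over 172 would be (133 × 1 + 39 × 1.44)/172 = 1.10. The ratio becomes √[(172/133)/1.10] = 1.08, so the gain falls to about 8%.

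**Effect sizes in the documents.**

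- LEAN (Section I, 12): 5.6 − 1.7 = 3.9 kg; SD √[(4.2² + 3.7²)/2] = 3.96 kg.
- Half of LEAN: 1.95 kg, same SD.
- The earlier telephone exercise trial in newly diagnosed women (Background): −0.4 versus +0.5 kg, a 0.9 kg difference; SD √[(3.7² + 2.9²)/2] = 3.32 kg.

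**Power.** For the first two, power = Φ[δ/(σ√(2/n)) − 1.96], with n per arm. The 0.9 kg column uses the two-sample t test, which differs from this formula by about one percentage point or less.

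| Women with weight data | Missing share | 3.9 kg | 1.95 kg | 0.9 kg |
|---|---|---|---|---|
| 172 (all) | 0% | >99.9% | 90% | 42% |
| 133 (all Yale) | 23% | >99.9% | 81% | 34% |
| 106 (80% of Yale) | 38% | 99.9% | 72% | 28% |
| 80 (60% of Yale) | 54% | 99.3% | 60% | 22% |
| 53 (40% of Yale) | 69% | 94.9% | 44% | 16% |

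The attendance levels are assumptions, because the documents give none. The difference detectable with 90% power, (1.96 + 1.28) × 3.96 × √(2/n), is 1.96 kg with 172 women and 2.22 kg with 133.

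**The larger-than-LEAN argument.** LEAN had 100 women (Background). 100/133 = 75%, so if fewer than about three quarters of the Yale target are measured, the weight analysis is smaller than LEAN and the stated reason for sufficient power no longer applies.

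**The case against.** Several points on the other side stand.

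- **Primary outcomes.** A reader might infer that women without a BMI drop out of the primary analyses, against intention to treat. The documents do not support this. RDI is tested by t test and by a Mantel-Haenszel test on stratification factors; endocrine adherence is compared by simple logistic regression. None uses BMI. The multivariable adherence model is labelled supportive, BMI is only to be examined as a covariate, and nothing says that missing covariates lead to deletion.
- **No weight at all.** A reader might also infer that all 39 women would have no weight at any visit. Only DFCI is barred throughout; other remote women may attend later visits, and record weight is planned at year 5. The split of the 39 between DFCI and Columbia is not given.
- **Power.** The closest planning basis is LEAN, the diet-and-exercise programme adapted here, and power for its difference survives even poor attendance. The 0.9 kg figure comes from an exercise-only trial of 50 women, and the fix would not make that comparison well powered.
- **Bias between arms.** Missingness by site or date is not missingness by arm. Section I, 12 assumes missing at random, looks for predictors of missingness and considers sensitivity analyses for data not missing at random.
- **Standardization.** Weighing in light clothing without shoes is a defensible choice that clinic scales will not match. The DXA measures stay Yale-only whatever is done.
- **Effort.** EPIC is described as on a Yale-New Haven Hospital server. Columbia records are requested at the end of chemotherapy, and DFCI staff are described as collecting chemotherapy completion data. Later weights from those sites need further requests.

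These limit the harm. They do not explain why record weight is acceptable at year 5 but is not a backup earlier.

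**Conclusion.** The point holds as a low-cost improvement to a secondary outcome. About 23% of the target sample would generally lack a measured baseline weight, and refusals and the pandemic pause add to that. The consequence is a confidence interval up to 14% wider with full Yale attendance, lower power for effects smaller than LEAN's, and an analysis set selected by site, date and ability to attend. The source of BMI for supportive adjusted models is also unstated.

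These sizes assume recruitment to the stated targets, equal arms among women measured, SDs like those of the earlier trials, and record weights as precise as study weights. The recovery assumes that clinic weights were recorded near each timepoint; the visit schedule makes this likely but the documents do not establish it.

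**What to change.** Where no study measurement exists, abstract height and the clinic weight closest to each of four timepoints from the medical record, at all sites: baseline (before or at the first infusion), end of chemotherapy, year 1 and year 2. Record the date and source of each value. Prefer the study-measured value when both exist. Repeat the Aim 2b weight and BMI analysis with study-measured values only as a sensitivity analysis. State that BMI at diagnosis comes from the record when no study value exists.

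The cost is a few added fields in an abstraction already under way, plus requests for year-1 and year-2 records from the non-Yale sites, with a check that the Columbia release covers them. The work can be done retrospectively, so visits already missed do not rule it out. The downside is less standardized weights, which the source flag and sensitivity analysis make visible.
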